7.0 MEASUREMENT OF EFFECT

7.1 Antitumor Effect- Solid Tumors

Immunotherapy drugs such as nivolumab can initially cause inflammation in the early stages of treatment. Immune-related RECIST (irRECIST) utilizes RECISTv1.1 but considers an inflammatory response (or "pseudo-progression") as normal. The main difference between RECISTv1.1 and irRECIST is that patients can stay on trial after the first progressive disease (PD) assessment (as per RECISTv1.1) if using immune-related RECIST criteria. This PD per RECISTv1.1 is then re-labeled as immune related stable disease (irSD) per irRECIST and requires addition of unidimensional measurements of all new lesions (that meet the definition of target lesion) to be added to the sum of longest diameters (SLD) calculation for response assessment. Importantly, immune-related progression (irPD) must be confirmed by a follow-up scan at least 4 weeks (within 4-8 weeks) following the initial PD/irSD assessment in order to take the patient off the trial.

Subjects that are deemed to have clinical progression and/or unstable should not be continued on therapy after PD (per RECISTv1.1) and are therefore not required to have repeat tumor imaging for confirmation as per irPD definition. It is at the discretion of the treating investigator whether to continue a subject on study treatment until repeat confirmatory imaging is obtained. This clinical judgment decision by the site investigator should be based on the subject's overall clinical condition, including performance status, clinical symptoms, and laboratory data.

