2.5 Secondary Endpoints

2.5.1 To assess the objective response rate (complete response and partial response) by RECIST 1.1 in metastatic renal cell cancer to ESK981 monotherapy.

2.5.2 To determine frequency and severity of adverse events by CTCAE criteria of ESK981 in patients with metastatic renal cell carcinoma.

2.5.3 To evaluate secondary efficacy measures such as overall survival, progression free survival, duration of therapy, duration of response to ESK981 monotherapy in Cohort A and to the combination in Cohort B; response by combined RECIST v1.1 and irRECIST and irRECIST progression free survival (Cohort B only).

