7.1.4 Response Criteria

7.1.4.1 Evaluation of Target Lesions

Patients will be evaluated according the following RECISTv1.1 response:

Complete Response (CR): Disappearance of all target lesions, determined by two separate observations conducted not less than 4 weeks apart. There can be no appearance of new lesions.

Partial Response (PR): At least a 30% decrease in the sum of the longest diameter (LD) of target lesions, taking as reference the baseline sum LD. There can be no appearance of new lesions.

Progressive Disease (PD): At least a 20% increase in the sum of the LD of target lesions (with a minimum absolute increase of 5 mm), taking as reference the smallest sum LD recorded since the treatment started, or the appearance of one or more new lesions.

Stable Disease (SD): Neither sufficient shrinkage to qualify for PR (taking as reference the baseline sum LD) nor sufficient increase to qualify for PD (taking as reference the smallest sum LD since the treatment started).

For Cohort B only:

After the first PD assessment per RECISTv1.1 (=irSD per irRECIST), patients will be evaluated for irPD at least 4 weeks apart according to the following definition:

Immune-related Progressive Disease (irPD): At least a 20% increase in the sum of the LD of target lesions (with a minimum absolute increase of 5 mm), taking as reference the smallest sum LD recorded since the treatment started, or appearance of new lesions since the last evaluation.

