7.1.4.3 Evaluation of Best Overall Response

The best overall response is the best response recorded from the start of the treatment until disease progression/recurrence (taking as reference for progressive disease the smallest measurements recorded since the treatment started). The patient's best response assignment will depend on the achievement of both measurement and confirmation criteria.

Evaluation as per combined RECISTv1.1/irRECIST

Target Lesions	Non-Target Lesions	New Lesions	Overall Response per RECISTv1.1	Overall Response per irRECIST (Cohort B only)	Confirmed Response for this Category Requires:
CR	CR	No	CR	NA	>4 wks. confirmation
CR	CR Non-CR/PD	No	PR	NA	>4 wks. confirmation
PR	CR Non-CR/PD	No			
SD	CR Non-CR/PD	No	SD	NA	Documented at least once \geq 4 wks. from baseline
PD	Any	Any	PD	irSD	>4 wks. confirmation
Any	PD*	Any			
Any	Any	Yes			
PD	Any	Any	NA	irPD	No further confirmation required
Any	PD*	Any			
Any	Any	Yes			

* Only in exceptional circumstances, unequivocal progression in non-target lesions may be accepted as disease progression.

Note: Patients with a global deterioration of health status requiring discontinuation of treatment without objective evidence of disease progression at that time should be reported as "*symptomatic deterioration*". Every effort should be made to document the objective progression even after discontinuation of treatment.

NA=not applicable

Note: If subjects respond to treatment and are able to have their disease resected, the patient's response will be assessed prior to the surgery.

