7.1.4.4 Treatment Beyond Progression – Cohort B only

Accumulating evidence indicates a minority of subjects treated with immunotherapy may derive clinical benefit despite initial evidence of PD.

Subjects treated on Arm B will be permitted to continue study treatment beyond initial RECISTv1.1 defined PD, assessed by the investigator, as long as they meet the following criteria:

- Investigator determined clinical benefit
- Tolerance of study drug
- Stable performance status

- Treatment beyond progression will not delay an imminent intervention to prevent serious complications of disease progression (e.g., CNS metastases)

A radiographic assessment/ scan should be performed within 4-8 weeks of initial investigator-assessed progression to determine whether there has been a decrease in the tumor size or continued PD (termed irPD). The assessment of clinical benefit should be balanced by clinical judgment as to whether the subject is clinically deteriorating and unlikely to receive any benefit from continued treatment.

If the investigator feels that the subject continues to achieve clinical benefit by continuing treatment, the subject should remain on the trial and continue to receive monitoring according to the Time and Events Table (Section 6.1).

Immune-related Progressive Disease (irPD): For the subjects who continue study therapy beyond progression, further progression is defined as an additional 10% increase in tumor burden with a minimum 5 mm absolute increase from time of initial PD, unequivocal worsening of NT lesions, or appearance of new lesions since the last evaluation. This includes an increase in the sum of diameters of all target lesions and/ or the diameters of new measurable lesions compared to the time of initial PD. Study treatment should be discontinued permanently upon documentation of further progression (i.e. irPD).

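### Cohort B's combined RECIST/irRECIST response endpoint has no category for a response after first progression, and it labels every first progression irSD

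*Combined protocol and SAP*

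**What the plan says.** Section 2.5 (item 2.5.3) lists among the secondary efficacy measures "response by combined RECIST v1.1 and irRECIST and irRECIST progression free survival (Cohort B only". The scoring rules are spread over Section 7:

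- **Section 7.1.** At first progression, "This PD per RECISTv1.1 is then re-labeled as immune related stable disease (irSD) per irRECIST". New measurable lesions are added to the sum, and irPD has to be confirmed by a scan 4 to 8 weeks later. Patients judged to be progressing clinically or unstable come off treatment and "are therefore not required to have repeat tumor imaging for confirmation as per irPD definition".
- **Section 7.1.4.1.** The same relabelling: "After the first PD assessment per RECISTv1.1 (=irSD per irRECIST), patients will be evaluated for irPD at least 4 weeks apart".
- **Section 7.1.4.3.** The table is introduced by "Evaluation as per combined RECISTv1.1/irRECIST". Its column "Overall Response per irRECIST (Cohort B only") reads NA on the CR, PR and SD rows. It reads irSD for first progression by any of three routes (target lesions, non-target lesions, new lesions) and irPD for the same routes on the later assessment. irCR and irPR appear nowhere in the protocol. On best response: "The best overall response is the best response recorded from the start of the treatment until disease progression/recurrence". The section adds that the assignment depends on confirmation as well as measurement.
- **Section 7.1.4.4.** A patient treated beyond progression is rescanned within 4 to 8 weeks "to determine whether there has been a decrease in the tumor size or continued PD (termed irPD").

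The primary endpoint (Sections 2.4 and 11.0) is RECIST 1.1 response only. Section 11.4 names no analysis of irRECIST response.

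**The concern.** An immune-related response criterion is added so that benefit after apparent progression can be recorded. Here the repeat scan has two possible findings, shrinkage or further progression, and only the second has a name. The combined endpoint would therefore report the same responders as RECIST v1.1, whatever happened after first progression. A reader could take that as evidence that treatment beyond progression produced no late responses, when the scoring had no place to put them.

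The automatic irSD label works in the other direction. It applies whatever the extent of growth, so a patient who progresses and is never rescanned can be tabulated under irRECIST as stable.

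**Working it through.** **Step 1: the plan's own figures.** The Cohort B design (Section 11.1) stops at 4 or fewer responses in 17 and succeeds at 14 or more in 36.

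- Probability of early termination = P(X ≤ 4 | n = 17, p = 0.25) = 0.574 (plan: 0.57).
- P(success | p) = Σ over x = 5 to 17 of Bin(x; 17, p) × P(Bin(19, p) ≥ 14 − x). This gives 0.8002 at p = 0.45 (plan: 80% power) and 0.0437 at p = 0.25 (plan: 5% limit).

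The figures reproduce. They use RECIST v1.1 responses only; no irRECIST entry enters them.

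**Step 2: patient courses traced through the table.** Rows 2 to 4 take patients whose first post-baseline finding is progression.

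| Course | RECIST v1.1 best response | irRECIST entries | Combined endpoint |
|---|---|---|---|
| 1. CR or PR before any progression | CR or PR | NA | Counted, through RECIST |
| 2. PD, treated on, sum later at least 30% below baseline | PD | irSD, then no entry | Not counted |
| 3. PD, then progression on the repeat scan | PD | irSD, then irPD | Not a responder; best irRECIST response unclear |
| 4. PD, clinical progression, no repeat scan | PD | irSD only | Not a responder; only irRECIST label is stable |

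In row 2, RECIST best response is closed at progression, and PR is also barred if a new lesion has appeared. So irRECIST adds no responder to RECIST v1.1.

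**Step 3: size for late responders.** The documents give no expected number, so these counts are assumptions. Start from 14/36 = 38.9% (exact 95% CI 23.1 to 56.5) and add patients who respond only after first progression:

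- 1 more: 15/36 = 41.7%
- 2 more: 16/36 = 44.4%
- 3 more: 17/36 = 47.2%

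Under the table as written, all three stay at 14/36.

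**Step 4: size for primary progressors.** Assume 6, 9 or 12 of 36 progress at the first scan. RECIST best response is PD in 16.7%, 25.0% or 33.3%. Under irRECIST the answer depends on the entry in the table's confirmation column for the PD/irSD row, which asks for more than 4 weeks' confirmation without saying whether PD or irSD is being confirmed.

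- *irSD stands once recorded:* best response irPD is 0/36 in every case. If irSD is counted as stable disease, 36/36 = 100% (95% CI 90.3 to 100) have a best result better than progression, against 83.3%, 75.0% or 66.7% by RECIST.
- *irSD itself needs confirming:* anywhere from 0 to all of the 6, 9 or 12 have best response irPD, depending on how many are rescanned. Those not rescanned have no confirmed irRECIST category.

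**Step 5: the two irPD definitions.** Section 7.1.4.1 uses a 20% increase over the smallest sum. Section 7.1.4.4 uses an additional 10% from the time of initial PD. Each has a 5 mm minimum. A patient with target-lesion PD whose sum is unchanged on the repeat scan is still at least 20% above the smallest sum, so meets the first definition. The increase since initial PD is 0%, so the patient does not meet the second.

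**The case against.** Several points against a stronger reading are sound.

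- **Best response depends on confirmation.** A reader might infer that no patient can ever have irPD as best response. Section 7.1.4.3 does not support that as a certainty, because the confirmation column can be read as requiring irSD to be confirmed. What stands is an ambiguity, and the section gives no separate best-response rule for irRECIST.
- **The endpoint is combined.** Patients who respond before progression still count, and primary progressors still show as PD in the RECIST column. The defect lies in what irRECIST adds.
- **Rescanning is not required, but it is not barred.** A reader might infer that clinical progressors can never be scored irPD. Footnote 6 in Section 6.1 continues tumor assessments and captures routine imaging in follow-up, so a later scan may document it.
- **The 30% rule may be implied.** Section 7.1 says irRECIST builds on RECIST v1.1, and Section 7.1.2 has response calculated with the new lesions included. The measurements will exist, so it goes too far to say that the trial could never tell whether late shrinkage occurred. But no reference sum or category is given for it and the table says NA, so the rule would have to be chosen after the data are seen.
- **Leak into the primary endpoint.** A reader might infer that late shrinkage could be entered on the PR row and move 4/17 to 5/17, or 13/36 to 14/36. That would break the plan: best response closes at progression, and the PR rows require no new lesions.

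This is also a descriptive secondary endpoint with no named analysis, which limits its weight but does not make the scoring work.

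**Conclusion.** The point holds for the Cohort B secondary endpoint of combined response. As written, irRECIST cannot add a single responder to RECIST v1.1, although the protocol schedules a scan to look for shrinkage after first progression. On the assumed counts, one to three late responders would raise the response rate by 2.8 to 8.3 percentage points (1/36 to 3/36), none of which would be recorded. Only patients treated beyond first progression are at risk of this, and the documents do not say how many to expect.

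The automatic irSD label is a second, smaller defect. It leaves patients with no repeat scan labelled only as stable, and it leaves the best irRECIST response after irSD then irPD undetermined.

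The primary RECIST 1.1 response rate, the 4/17 and 14/36 rules and the power are unaffected if the plan is followed. The change should be made, but it does not threaten the trial's main conclusion.

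**What to change.** For outcome classification only:

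1. In the Section 7.1.4.3 table, add irCR and irPR rows for Cohort B after first RECIST progression. Use the total sum, including new measurable lesions, against the baseline sum, with the 30% threshold already in Section 7.1.4.1 for irPR and disappearance of all lesions for irCR.
2. In Sections 7.1, 7.1.4.1 and 7.1.4.3, record first progression as unconfirmed instead of automatically irSD. Assign irSD, irPR, irCR or irPD from the repeat scan. Report patients with no repeat scan as a separate group, progression not confirmed, and do not count them as stable. They should not be scored irPD, because Section 7.1 requires a follow-up scan for that.
3. State that irRECIST categories never change RECIST v1.1 best response. Define combined response as RECIST v1.1 CR or PR, or irCR or irPR, and repeat the definition in Section 11.4.
4. Reconcile the irPD definitions in Sections 7.1.4.1 and 7.1.4.4. Item 2 and irRECIST progression-free survival both depend on which one applies, and so does the treatment decision in Section 7.1.4.4; the choice is for the sponsor.

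The cost is a few table rows and sentences. The 4 to 8 week scan is already planned for patients treated beyond progression, so no procedure is added. The one downside is a slightly less favorable irRECIST stable-disease count.

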7.1.1 Definitions

Evaluable for toxicity. All patients will be evaluable for toxicity if they have received at least 1 dose of ESK981.

Evaluable for objective response. Only those patients who have measurable disease present at baseline, have received at least 2 cycle(s) of therapy, and have had their disease re-evaluated will be considered evaluable for response. These patients will have their

response classified according to the definitions stated below. (Note: Patients who exhibit objective disease progression prior to the end of cycle 2 will also be considered evaluable.)

7.1.2 Disease Parameters

Measurable disease. Measurable lesions are defined as those that can be accurately measured in at least one dimension (longest diameter in the plane of measurement is to be recorded) with a minimum size of:

- 10mm by CT scan (irrespective of scanner type) for studies with a slice thickness of $\leq 5\text{mm}$ or twice the slice thickness or MRI
- 10mm caliper measurement by clinical exam (lesions which cannot be accurately measured with calipers should be recorded as non-measurable)
- 20mm by chest X-ray (if clearly defined and surrounded by aerated lung)

All tumor measurements must be recorded in millimeters (or decimal fractions of centimeters).

Malignant lymph nodes: To be considered pathologically enlarged and measurable, a lymph node must be $\geq 15\text{mm}$ in short axis when assessed by CT scan (CT scan slice thickness recommended to be no greater than 5 mm). At baseline and in follow-up, only the short axis will be measured and followed.

Note: Tumor lesions that are situated in a previously irradiated area will only be considered measurable, if they have had subsequent progression by at least 5 mm.

Non-measurable disease. All other lesions (or sites of disease), including small lesions ($<10\text{ mm}$ using CT scan), are considered non-measurable disease. Bone lesions without measurable soft tissue component, leptomeningeal disease, ascites, pleural/pericardial effusions, lymphangitis cutis/pulmonis, inflammatory breast disease, abdominal masses (not followed by CT or MRI), and cystic lesions are all non-measurable.

Target lesions. All measurable lesions up to a maximum of 2 lesions per organ and 5 lesions in total should be identified as **target lesions** and recorded and measured at baseline. Target lesions should be selected on the basis of their size (lesions with the longest diameter), be representative of all involved organ, but in addition should be those that lend themselves to reproducible repeated measurements.

For Cohort B only: If a non-nodal lesion is either not present or is initially measured with longest diameter $<10\text{mm}$ as a non-target then grows to $\geq 10\text{mm}$ after baseline, this lesion then becomes a new target lesion as per irRECIST criteria. The non-nodal longest diameter is then added to the sum of diameters, and patient response is calculated with the new lesion.

Lymph nodes merit special mention since they are normal anatomical structures which may be visible by imaging even if not involved by tumor. Pathological nodes which are defined as measurable and may be identified as target lesions must meet the criterion of a short axis of $\geq 15\text{mm}$ by CT scan. Only the short axis of these nodes will contribute to the baseline sum. The short axis of the node is the diameter normally used by radiologists to judge if a node is involved by solid tumor. Nodal size is normally reported as two dimensions in the plane in which the image is obtained (for CT scan this is almost always the axial plane; for MRI the plane of acquisition may be axial, sagittal or coronal). The smaller of these measures is the short axis. For example, an abdominal node which is reported as being $20\text{mm} \times 30\text{mm}$ has a short axis of 20mm and qualifies as a malignant, measurable node. In this example, 20mm should be recorded as the node measurement. All other pathological nodes (those with short

axis ≥ 10 mm but < 15 mm) should be considered non-target lesions. Nodes that have a short axis < 10 mm are considered nonpathological and should not be recorded or followed. A sum of the diameters (longest for non-nodal lesions, short axis for nodal lesions) for all target lesions will be calculated and reported as the baseline sum diameters. If lymph nodes are to be included in the sum, then as noted above, only the short axis is added into the sum. The baseline sum diameters will be used as reference to further characterize any objective tumor regression in the measurable dimension of the disease.

For Cohort B only: If a non-target lymph node grows to ≥ 15 mm after baseline, this node then becomes a new target lesion as per irRECIST. The nodal short axis is then added to the sum of diameters, and patient response is calculated with the new lesion.

Non-target lesions. All other lesions (or sites of disease) including pathological lymph nodes should be identified as non-target lesions and should also be recorded at baseline. Measurements are not required and these lesions should be followed as 'present', 'absent', or in rare cases 'unequivocal progression' (more details to follow). In addition, it is possible to record multiple non-target lesions involving the same organ as a single item on the case record form (e.g. 'multiple enlarged pelvic lymph nodes' or 'multiple liver metastases').

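### Cohort B adds the full diameter of a baseline non-target lesion to a sum whose references never contained it, and the text does not say that this stays out of RECIST v1.1

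*Combined protocol and SAP*

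**What the plan says.** Two paragraphs of section 7.1.2, marked for Cohort B only, set the rule. The non-nodal one covers a lesion that is "either not present or is initially measured with longest diameter" below 10 mm as a non-target and later measures 10 mm or more. It says that "this lesion then becomes a new target lesion as per irRECIST criteria" and continues: "The non-nodal longest diameter is then added to the sum of diameters, and patient response is calculated with the new lesion". For a non-target node that reaches 15 mm, "this node then becomes a new target lesion as per irRECIST", and the same consequence follows: "The nodal short axis is then added to the sum of diameters, and patient response is calculated with the new lesion".

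Section 7.1 describes the method more narrowly. Once a RECIST v1.1 progression has been re-labelled as immune-related stable disease, the method "requires addition of unidimensional measurements of all new lesions" to the sum.

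The reference sums are defined elsewhere. Section 7.1.2 builds the baseline sum from baseline target lesions only. Section 7.1.4.1 defines partial response as "At least a 30% decrease in the sum of the longest diameter (LD) of target lesions, taking as reference the baseline sum LD". It defines progression as a rise of at least 20% and 5 mm over the smallest sum recorded on treatment.

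The primary endpoint is the RECIST 1.1 objective response rate for the combination (section 2.4.1). Section 2.5.3 lists irRECIST PFS and combined RECIST v1.1/irRECIST response as secondary endpoints in Cohort B.

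**The concern.** A percentage change in a sum of diameters has meaning only if the sum and its reference cover the same lesions. For a lesion absent at baseline, adding the whole diameter is coherent, because its earlier size was zero. For a lesion present at baseline as a non-target it is not, because the earlier 9 mm (or 14 mm for a node) is missing from the reference and is counted as growth. Without the rule, the same lesion would stay non-target, and section 7.1.4.2 would require unequivocal progression before calling it PD.

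Two things are at stake. If the rule is applied to RECIST v1.1, it can produce progression or block a partial response in the primary endpoint. There the decision boundaries are 5 of 17 responses to continue and 14 of 36 for success (section 11.1), so one patient at a boundary changes the outcome. If it is applied only to irRECIST, it can produce irPD, which section 7.1.4.4 ties to permanent discontinuation of treatment.

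**Working it through.** The plan gives no figure for the effect of this rule, so there is none to reproduce. The check applies the plan's own thresholds.

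**Inputs.** Added diameter a = 10 mm (non-nodal) or 15 mm (node), from 7.1.2. PD: at least +20% and +5 mm over the nadir N, from 7.1.4.1. PR: at least −30% from the baseline sum B, from 7.1.4.1. irPD after initial progression: at least +10% and +5 mm over the sum at that time, S, from 7.1.4.4. Assumptions: the lesion grows from 9 to 10 mm (node 14 to 15 mm) and all other targets are unchanged.

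**Progression from the addition alone.** a/N ≥ 0.20 gives N ≤ a/0.20.
- Non-nodal: 10/0.20 = 50 mm. At 50 mm the rise is 20.0%; at 51 mm it is 19.6%, which is not PD.
- Node: 15/0.20 = 75 mm.

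**irPD under 7.1.4.4, if the crossing occurs after initial progression.** a/S ≥ 0.10 gives S ≤ a/0.10.
- Non-nodal: 10/0.10 = 100 mm.
- Node: 15/0.10 = 150 mm.

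**Partial response, if the rule is applied to RECIST v1.1.** With C the current sum of the original targets, PR needs C + a ≤ 0.70B. The original targets must therefore shrink by 0.30 + a/B instead of 0.30.

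| Baseline sum B | 50 mm | 60 mm | 100 mm | 150 mm |
|---|---|---|---|---|
| Non-nodal, a = 10 | 50.0% | 46.7% | 40.0% | 36.7% |
| Node, a = 15 | 60.0% | 55.0% | 45.0% | 40.0% |

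Example: B = 60 and C = 42 mm is −30.0%, a PR. Adding 10 mm gives 52 mm, which is −13.3% from baseline and 10/42 = +23.8% over the nadir. That scan is scored as PD.

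**Same lesions in sum and reference.** Put the earlier diameter into the reference.
- Nadir 50 + 9 = 59 mm, now 60 mm: +1.7%, not PD.
- Node: 75 + 14 = 89 mm, now 90 mm: +1.1%, not PD.
- B = 100, C = 62 mm: the written rule gives 72/100 = −28.0% (PR lost). The matched reference gives 72/109 = −33.9% (PR kept).
- B = 60, C = 42 mm: the matched reference gives 52/69 = −24.6%, so this borderline PR is not met under this option either. It stands only if the lesion is left out of the sum.

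**Two irPD definitions.** Suppose the first progression comes from the added 10 mm and nothing grows afterwards. At the confirmatory scan the sum is still at least 20% above the nadir, so the 7.1.4.1 definition of irPD is met on that criterion. It is 0% above the sum at initial progression, so the 7.1.4.4 size criterion is not met. The two sections classify the same scan differently.

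**The case against.** The strongest reply is that the rule never touches RECIST v1.1. Both Cohort B paragraphs carry the irRECIST label. Section 7.1 places the addition after a RECIST v1.1 progression, and 7.1.4.1 starts irPD evaluation only after that event. The table in 7.1.4.3 has a separate irRECIST column, marked not applicable in the CR, PR and SD rows. Best overall response is recorded only until progression, so on this reading the primary response count is settled before the rule operates. The table defines no immune-related partial response either, so the PR figures above would then correspond to no defined outcome.

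Much of this stands, and it is probably the intent. It does not close the point. The operative sentences refer to patient response without naming a criterion or a time. They sit inside the target-lesion definition on which 7.1.4.1 bases RECIST v1.1 CR, PR and PD, and a non-target lesion can cross the threshold before any progression. Two sites could score the same scan differently on the primary endpoint. The narrow reading also leaves the mismatch between sum and reference in place for irRECIST.

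A reader might infer three stronger claims that the documents do not support:
- That the primary response rate is shown to be biased downward. This depends on the broad reading and on an unknown frequency of crossing.
- That an established partial response is erased. A confirmed PR stands as best overall response; only an unconfirmed or not-yet-reached PR is exposed.
- That Cohorts A and B become non-comparable in a way that matters. No comparison is planned; section 11.4 reports each cohort separately.

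**Conclusion.** The point holds in a limited form. Followed as written, the rule scores 1 mm of growth in a baseline non-target lesion as 10 or 15 mm. With other targets stable, that suffices for PD at a nadir sum of 50 mm or less (node: 75 mm). It suffices for irPD under 7.1.4.4 at a sum at initial progression of 100 mm or less (node: 150 mm) when the crossing comes later.

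On the broad reading, which the wording permits, it can create progression or prevent an unconfirmed or not-yet-reached PR in the primary endpoint. On the narrow reading, which sections 7.1 and 7.1.4.3 suggest, it affects irPD, irRECIST PFS, and combined RECIST v1.1/irRECIST response so far as that rests on the irRECIST sum. All of these are secondary.

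Nothing in the documents indicates how often a baseline non-target lesion would cross the threshold, so no effect on the response rate or on power is claimed.

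**What to change.** 1. In both Cohort B paragraphs of section 7.1.2, state that RECIST v1.1 response and PFS use only the target lesions fixed at baseline, and that the RECIST v1.1 sum is kept separate from the irRECIST sum.
2. Reconcile section 7.1 (new lesions), section 7.1.2 (baseline non-targets that cross the threshold) and the two irPD definitions in 7.1.4.1 and 7.1.4.4, so that the irRECIST sum and its reference cover the same lesions. Two coherent routes exist: do not add lesions already present at baseline, or include their earlier diameter in the reference. Because irPD determines discontinuation of treatment, the choice belongs to the sponsor.

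The cost is two edited paragraphs, the reconciliation of the irPD text, and recalculation of sums from recorded diameters for any Cohort B scans already read. No new scans are needed. One limit applies to the second route: section 7.1.2 does not require non-target lesions to be measured, so their earlier diameters may not be on record.
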